12 APPENDICES

APPENDIX 1 PROTOCOL HISTORY

Document	Date	Global/Country/Site Specific
Original Protocol	23 Jan 2018	Global
Amendment 1	27 Sep 2018	Global

APPENDIX 2 PARENTERAL NUTRITION/INTRAVENOUS OPTIMIZATION

After signing the ICF, the investigator will determine if the subject's PN/IV volume produces an appropriate urine output target of 1.0 L/day to 2.0 L/day. If the output is within the range, the subject will enter the stabilization period. If the output is outside the range, the subject's PN/IV volume should be adjusted appropriately to reach the targeted urine output of between 1.0 L/day to 2.0 L/day while keeping the subject adequately hydrated and nourished. For example, if 48-hour urine output is:

- <1.0 L/day, then PN/IV should be increased.
- >2.0 L/day, then PN/IV should be reduced.

If it is not possible to keep the subject adequately hydrated and nourished within the targeted urine output range, the minimally tolerated PN/IV volume should be documented. Keep in mind the following:

- During optimization, total weekly PN/IV volume should be adjusted in increments or decrements of 10-30% of the screening volume.
- Parenteral nutrition constituents may be adjusted at the discretion of the investigator.
- Subjects should be encouraged to maintain a stable normal or hyperphagic diet (eg, at least 1.3 times the estimated basal metabolic rate).

Steps for adjusting PN/IV volume:

1. **Screening and Optimization Visits:** Subjects will be assessed at planned intervals for hydration and nutrition. The subject will make all measurements of 48-hour I/O at home immediately prior to the scheduled visits. Blood and urine samples will be collected at each visit to evaluate hydration and nutrition. All blood and urine samples should be taken at a consistent time period throughout the study that is convenient for the subject and site staff.
2. **Interim Safety Evaluations:** If any PN/IV adjustments are made, the clinical effect and the health status of the subject will be assessed 5 to 7 days after the adjustment is implemented. Laboratory safety samples should be evaluated following a PN/IV adjustment (see [Table A3](#)), accompanied by determination of 48-hour I/O and symptoms of dehydration. At the interim safety visit, PN/IV should be increased if the decrease was not tolerated. No further reductions to PN/IV volume are made at the interim safety visit.
3. Maintain the PN/IV level until the next scheduled optimization visit.
4. Repeat steps 1 through 3 until the subject achieves an optimized volume of PN/IV indicated by targeted urine output of 1.0 L/day to 2.0 L/day. If a subject has not achieved an optimal tolerated volume of PN/IV after 8 weeks, consult the sponsor's Medical Monitor.
5. **PARENTERAL NUTRITION STABILIZATION:** Once an optimal tolerated PN/IV volume has been reached, the subject will begin the 4-week minimum stabilization period. No further PN/IV adjustments should take place during this time period.

APPENDIX 3 PARENTERAL NUTRITION/INTRAVEOUS ADJUSTMENT DURING TREATMENT PERIOD

Points to keep in mind when adjusting PN/IV volume during dosing:

- There will be no PN/IV reduction attempts at baseline and Week 1.
- Parenteral nutrition/intravenous reductions target urine output increases of at least 10% over baseline.
- Attempts to reduce PN/IV will be made at dosing Weeks 2, 4, 8, 12, 16, and 20.
- Parenteral nutrition/intravenous adjustments are targeted to be at least 10% but no more than 30% of **baseline** PN/IV level.
- Adjustments should be based on the actual PN/IV volume the subject infuses. Subjects should remain compliant with the PN/IV prescription during the length of the study.
- Parenteral nutrition/intravenous constituents may be adjusted at the discretion of the investigator.
- Criteria for PN/IV adjustments are in [Table A1](#).
- During the 48-hour I/O measurement period, oral intake should be consistent with baseline oral intake.
- If there is a change in oral intake, the investigator should consider this when adjusting the PN/IV volume.
- Subjects should be encouraged to maintain a stable normal or hyperphagic diet.
- Frequent checks will be made to ensure the adjustments are safe (see [Table A2](#)).
- Subjects who fail to maintain a PN/IV reduction due to a medical necessity (eg, sepsis or hospitalization due to an AE) will not be considered a failure of reduction.
- If at any time, the algorithm cannot be followed, consult with the sponsor's Medical Monitor.

Table A1 Parenteral Nutrition Adjustments at Scheduled Clinic Visits based on 48-hour Urinary Output

Urine Output	Parenteral Nutrition/Intravenous Action
Below 1.0 L/day or target based on stabilized urine output	Increase PN/IV by at least 10% (Week 2) or to previous level.
1.0 L/day or more and less than Baseline	If subject is dehydrated or inadequately nourished (see Table A2), increase PN/IV. If not, maintain PN/IV.
Baseline or more, and less than a 10% increase over Baseline	Maintain PN/IV
At least a 10% increase over Baseline	Reduce PN/IV by at least 10% of stabilized Baseline level up to a clinically appropriate amount (maximum of 30%).

L=liter; PN/IV=parenteral nutrition/intravenous (volume)

Table A2 Targeted Criteria for Hydration and Nourishment at all Clinic Visits and Interim Safety Visits

Hydration Assessment	Hydration Adequate
Hematocrit	At or below ULN
Serum BUN	At or below ULN
Serum creatinine	At or below 2xULN
Urine sodium	20 mmol/L or more
Clinical signs and symptoms of dehydration	Absent
Body weight change in 4 weeks	Change less than 1.5 kg

BUN = blood urea nitrogen; ULN = upper limit of normal

Note: In combination with [Table A1](#), any one of the above criteria determines dehydration.

Steps for adjusting PN/IV volume:

1. **DOSING WEEKS 2, 4, 8, 12, 16, and 20:** Subjects will be assessed at planned intervals for hydration and nutrition. The subject will make all measurements of 48-hour I/O at home prior to the scheduled visits. Blood and urine samples will be collected to evaluate hydration and nutrition (see [Table A2](#)). All blood and urine samples should be taken at a consistent time period throughout the study, convenient for the subject and site staff.
2. **Parenteral Nutrition Changes:** Review [Table A1](#) and [Table A2](#) to take appropriate action.
3. **Interim Safety Evaluations:** If any PN/IV adjustments are made, the clinical effect and the health status of the subject will be assessed 5 to 7 days after the adjustment is implemented. Laboratory safety samples should be evaluated following a PN/IV adjustment (see [Table A3](#)), accompanied by determination of 48-hour I/O and symptoms of dehydration. At the interim safety visit, PN/IV should be increased if the decrease was not tolerated. No further reductions to PN/IV volume are made at the interim safety visit.

Table A3 Assessment of Tolerance of Pareneteral Nutrition/Intravenous Adjustments at Interim Safety Visits

Urine Output, Hydration and Nutrition	Pareneteral Nutrition/Intravenous Action
Output less than Baseline	Increase PN/IV to previous volume ^a
Baseline output or greater and subject is dehydrated (See Table A2)	Increase PN/IV to previous volume ^a
Baseline output or greater and subject is not dehydrated, but is inadequately nourished (See Table A2)	If possible, maintain PN/IV volume and increase nutrition. If not, increase PN/IV to previous volume ^a
Baseline output or greater and subject is adequately hydrated and nourished (See Table A2)	Maintain PN/IV

L=liter; PN/IV=parenteral nutrition/intravenous (volume)

^a If most recent reduction was greater than 10% due to a urine volume of more than 2 L/day, a more moderate increase in PN/IV is allowed.

4. Maintain the adjusted PN/IV level until the next scheduled visit.
5. Repeat steps 1 through 4 at each study visit as indicated per protocol.
 - a. It is preferred that when the total weekly PN/IV needs have been reduced to a level that safely allows for a day or days off PN/IV, the physician should consider instituting a day(s) off PN/IV.
 - b. If the total weekly PN/IV is only administered in 2 days, it is probably in the subject's best interest to be weaned off PN/IV completely. This is the 1 exception to the maximum 30% reduction guidance. This weaning should be done under the supervision of the investigator.
 - c. If the subject experiences symptoms of dehydration, the subject can be advised by the investigator to take extra IV fluid that will be included in the weekly PN/IV volume total.

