3.1.2 Treatment Period

Following the stabilization period, subjects will enter a 24-week dosing period, during which all subjects will receive teduglutide 0.05 mg/kg SC once daily. At each site visit during the treatment phase, efficacy (adjustments to PN/IV) and safety will be monitored.

Subjects will have blood samples taken for teduglutide PK analysis at predose, at 15, 30 minutes and 1, 2, 3, 4, 6, 8, 10, and 12 hours post dose at the baseline visit (Visit 2). Subjects will also have blood samples taken for teduglutide PK analysis at predose and 1 and 2 hours post dose at Week 4 (Visit 5) or Week 12 (Visit 7) of the treatment period.

All subjects who complete the study may participate in a long-term extension study in which eligible subjects will continue to receive teduglutide.

Schedules of evaluations for the Treatment Period can be found in [Table 2](#). Procedures to adjust or reduce PN/IV volume during the Treatment Period is provided in [Appendix 3](#), and should be followed carefully throughout the study.

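### The weight row of Table A2 has no direction, so read literally a gain of 1.5 kg or more in 4 weeks counts as dehydration and can call for more PN/IV volume

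*Protocol*

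**What the plan says.** All references are to protocol Amendment 1, Appendix 3, unless stated. The January 2018 protocol has the same weight row and note in its Appendix 2.

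- **Table A2** covers clinic visits and interim safety visits, and its columns are headed in terms of hydration. Hematocrit and BUN must not exceed the ULN, creatinine must not exceed twice the ULN, urine sodium must reach 20 mmol/L, and clinical signs must be absent. For body weight over 4 weeks the entry is "Change less than 1.5 kg".
- **Note to Table A2:** "any one of the above criteria determines dehydration". Its opening words tie it to Table A1.
- **Table A1, row 2** (scheduled visit, output of 1.0 L/day or more but below baseline): "If subject is dehydrated or inadequately nourished (see Table A2), increase PN/IV. If not, maintain PN/IV". Rows 3 and 4, for output at baseline or more, do not refer to Table A2.
- **Table A3, row 2** (interim visit) has the condition, up to its closing bracket, "Baseline output or greater and subject is dehydrated (See Table A2". The action is to go back to the previous volume. Footnote a allows a smaller increase after a reduction of more than 10% that was made because urine volume exceeded 2 L/day.
- **Step 3:** after an adjustment the subject "will be assessed 5 to 7 days after the adjustment is implemented". The same step, like Section 7.2.2.2, ties an interim increase to a decrease that was not tolerated.
- **Status of the algorithm:** Section 3.1.2 refers sites to Appendix 3 for the adjustment procedures "and should be followed carefully throughout the study". The clause that sends sites to the Medical Monitor opens "If at any time, the algorithm cannot be followed".

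**The concern.** Five rows of Table A2 can fail only in the direction of dehydration. The weight row can also fail on a gain, and nothing elsewhere in the protocol or SAP limits it to loss or gives a rule for gain.

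Weight gain is a plausible result of treatment working. Section 1.1 describes these patients as struggling to maintain weight, Section 1.2 describes a drug that enlarges the absorptive surface, and Appendix 3 encourages a normal or hyperphagic diet. The printed rule can answer such a gain with more intravenous volume. For a loss, restoring volume is the cautious action. For a gain it is not, because it adds fluid to a subject whose weight is already rising.

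PN/IV volume is also what the trial measures (protocol Section 9.7, SAP v2.0 Section 6.1). A reduction undone for this reason therefore lowers the observed effect. If some investigators apply the row literally and others read it as loss, sites will treat the same findings differently.

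**Working it through.** The plan has no figure to reproduce here. The check runs the tables as a decision rule.

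**Step 1: what fails the weight row.** The limit is 1.5 kg (Table A2). Three readings are compared: absolute (|change| < 1.5 passes), signed (change < 1.5 passes) and loss only (loss < 1.5 passes).

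| 4-week change (kg) | Absolute | Signed | Loss only |
|---|---|---|---|
| −2.0 or −1.5 | fail | pass | fail |
| −1.4, 0 or +1.4 | pass | pass | pass |
| +1.5 or +2.0 | fail | fail | pass |

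A gain of 1.5 kg or more fails under both readings that the printed words allow. The signed reading would also let a loss of any size pass.

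**Step 2: what the tables then do.** The assumptions are a baseline output of 1.5 L/day (inside the 1.0 to 2.0 L/day target), the other five Table A2 rows adequate, Table A1 row 1 taken as output below 1.0 L/day, and the latest adjustment before an interim visit a reduction. The 10% threshold is 1.1 × 1.5 = 1.65 L/day. The literal rule is the absolute reading. Results for a gain of 1.5 or 2.0 kg:

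| Output (L/day) | A1 literal | A1 loss only | A3 literal | A3 loss only |
|---|---|---|---|---|
| 0.9 | increase | increase | previous volume (row 1) | previous volume (row 1) |
| 1.4 | **increase (row 2)** | **maintain** | previous volume (row 1) | previous volume (row 1) |
| 1.5 or 1.6 | maintain | maintain | **previous volume (row 2)** | **maintain** |
| 1.7 | reduce 10–30% | reduce 10–30% | **previous volume (row 2)** | **maintain** |

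At +1.4 kg the literal and loss-only rules agree everywhere. At −1.5 and −2.0 kg they also agree everywhere. The wording matters only in Table A1 row 2 and Table A3 row 2, and only for a gain of 1.5 kg or more.

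The last line also shows an inconsistency. At a scheduled visit, output at least 10% over baseline leads to a reduction without reference to weight. The same gain can then reverse that step at the interim visit.

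**Step 3: the link to the endpoint.** Response needs a reduction of at least 20% from baseline at both Weeks 20 and 24. As a constructed example, a subject already at 10% who takes a further 10% step is at 10 + 10 = 20% if the step is kept and at 10% if it is reversed. At the planned minimum of 5 subjects, one response is 1/5 = 20 percentage points. This shows how a result could change; it does not estimate how often.

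**The case against.** The strongest reply is that context supplies the direction. The columns and the note concern dehydration, and few physicians would call a subject dehydrated because weight rose while hematocrit, BUN, creatinine, urine sodium and clinical signs were all adequate. Step 3 supports this for interim visits, since stable output, normal tests and rising weight do not show that a decrease was not tolerated. This stands as a reason to expect that many investigators would not act on the literal row. It does not remove the defect. Table A3 row 2 states its action without that limit, and Section 7.2.2.2 asks for every attempt to follow the algorithm. The Medical Monitor route covers cases where the algorithm cannot be followed, and here it can be.

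Four narrower points also stand in part.

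- The note names only Table A1. However, Table A3 cites Table A2 directly, and the title of Table A2 includes interim visits.
- Footnote q to Table 2, Section 7.2.3.1 and Step 3 do not name weight among the interim measures. Section 7.2.3.4 speaks of each study visit. The interim path therefore applies only where weight is in fact measured.
- Table A1 row 2 applies only when output is already below baseline, so the gain is never the sole trigger there. The row also prints no amount for the increase.
- Table A3 row 2 only restores the volume in use before the latest step, and a later scheduled visit allows another attempt, except after Week 20.

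Reading the row as a test of nourishment does not help. Table A1 row 2 would still increase PN/IV, and Table A3 row 3 would call for more nutrition or the previous volume.

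A reader might infer that any gain of this size leads to more PN/IV at every visit. The tables do not say so: Table A1 rows 3 and 4 ignore Table A2, and output below baseline at an interim visit already restores volume under Table A3 row 1.

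**Conclusion.** The point holds as a defect in a stated rule. Followed as printed, the tables give the wrong action for a gain of 1.5 kg or more in two places: Table A1 row 2, and Table A3 row 2 where weight is measured. This rests on the literal text, on reading the note as failure of any one row, and on the other five rows being adequate.

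The size of the effect cannot be computed. The documents give neither the mean nor the spread of 4-week weight change, and no rate of such gains. A reader might infer that responses will be lost at some predictable rate. The documents do not support that, and the 20-point figure only says what one response is worth among 5 subjects. Enrollment is at least 5, so with more subjects one response is worth less. The trial is descriptive with no hypothesis test, so no test result is at stake. The correction is still worth making, because it concerns fluid given to subjects and the volume being measured, and it leaves the response to weight loss as it is.

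**What to change.** Change the weight row of Table A2 to: *Body weight loss in 4 weeks: less than 1.5 kg*. Add to the note that a gain of 1.5 kg or more is not dehydration and is not by itself a reason to increase PN/IV, but should prompt an assessment of fluid status. The action for a loss of 1.5 kg or more stays as under the absolute reading.

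The cost is one table row and one added sentence, by clarification letter or amendment, with no new procedure and no new variable.

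Three clarifications could go into the same edit but are not part of this point: say that the note applies to Table A3 as well as Table A1; say that nourishment is judged clinically, since Table A2 has no row labelled for it; and say in Table 2 footnote q whether weight is taken at interim visits.

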## **REVISION HISTORY**

Version	Issue Date	Summary of Changes
Final 1.0	12Dec2018	New Document

## ABBREVIATIONS

AE	Adverse Event
ALT	Alanine Aminotransferase, Equivalent To SGPT
AST	Aspartate Aminotransferase, Equivalent To SGOT
AUC	Area Under the Plasma Concentration-Time Curve
AUC 0-t	AUC From Zero to The Last Measurable Concentration
BLQ	Below the Lower Limit if Quantification
BMI	Body Mass Index
BUN	Blood Urea Nitrogen
CL/F	Apparent Clearance
C max	Maximum Plasma Concentration
CTMS	Clinical Trial Management System
CV	Coefficient of Variation
ECG	Electrocardiogram
eCRF	Electronic Case Report Form
EGD	Esophagogastroduodenoscopy
EOT	End of Treatment
ET	Early Termination
GI	Gastrointestinal
ICF	Informed Consent Form
ICH	International Conference on Harmonization
ITT	Intent-To-Treat
MedDRA	Medical Dictionary for Regulatory Activities
NCA	Non-compartmental Analysis
PK	Pharmacokinetics
PP	Per Protocol
PN/IV	Parenteral Nutrition/Intravenous
PT	Preferred Terms
SAE	Serious Adverse Event
SAP	Statistical Analysis Plan

SBS	Short Bowel Syndrome
SC	Subcutaneous
SI	Standard International
SOC	System Organ Class
$t_{1/2}$	Terminal-Phase Half-Life
$t_{max}$	Time to $C_{max}$
TEAE	Treatment Emergent Adverse Event
TESAE	Treatment Emergent Serious Adverse Event
ULN	Upper Limit of Normal
ULQ	Above the Upper Limit of Quantification
V/F	Apparent Volume of Distribution

## 1. INTRODUCTION

This statistical analysis plan (SAP) provides a technical and detailed elaboration of the statistical analyses of efficacy, safety and pharmacokinetic (PK) data (descriptive summaries only) as described in the final study protocol dated 23 Jan 2018. Specifications for tables, figures, and listings are contained in a separate document. Pharmacokinetics analyses (other than descriptive summaries) will be described in a separate [PK SAP](#).

## 2. OBJECTIVES, ESTIMAND(S), AND ENDPOINTS

### 2.1 Objectives

The objectives of this clinical study are to evaluate the safety, efficacy, and pharmacokinetics of teduglutide in Japanese subjects with short bowel syndrome (SBS) who are dependent on parenteral nutrition/intravenous (PN/IV) over a 24-week treatment period.

### 2.2 Estimand(s)

Absolute change from baseline in weekly PN/IV volume based on diary data at End of Treatment (EOT) in Japanese subjects with PN/IV – dependent SBS in the Intent-to-treat (ITT) Population.

Relative change from baseline in weekly PN/IV volume based on diary data at EOT in Japanese subjects with PN/IV – dependent SBS in the ITT Population.

Number/percentage of subjects who achieved at least 20% decrease from baseline in weekly PN/IV volume based on diary data at Week 20 and Week 24 in Japanese subjects with PN/IV – dependent SBS in the ITT Population.

Number/percentage of subjects who achieved at least 20% decrease from baseline in weekly PN/IV volume based on diary data at Week 20 and Week 24 in Japanese subjects with PN/IV – dependent SBS in the PP Population.

Number/percentage of subjects who achieve at least a 20% reduction from baseline in weekly PN/IV volume based on diary data at each visit in Japanese subjects with PN/IV – dependent SBS in the ITT Population.

## 2.3 Endpoints

### 2.3.1 Efficacy Endpoint(s)

The following efficacy endpoints will be analyzed:

- Absolute and relative change from baseline in weekly PN/IV volume by visit and at EOT.
- Percentage of subjects who achieve at least 20% reduction from baseline in weekly PN/IV volume at both Weeks 20 and 24.
- Percentage of subjects who achieve at least a 20% reduction from baseline in weekly PN/IV volume at each visit
- Change in days per week of PN/IV support from baseline by visit.
- Change in plasma citrulline from baseline by visit.
- Number of subjects who are able to completely wean off of PN/IV support.

### 2.3.2 Safety Endpoint(s)

The safety endpoints include adverse events (AEs), 12-lead electrocardiogram (ECG), vital signs, laboratory safety data, antibodies to teplizumab, and 48-hour urine output, body weight, body mass index (BMI) and gastrointestinal-specific tests.

### 2.3.3 Pharmacokinetic Endpoint(s)

The following parameters will be derived as described in a separate [PK SAP](#) and reported separately:

Area under the plasma concentration–time curve from zero to the last measurable concentration (AUC0–t)

Maximum plasma concentration (Cmax)

Time to Cmax (tmax)

terminal-phase half-life (t1/2)

Apparent clearance (CL/F)

[figure not shown]
Apparent volume of distribution (V/F)

### 3. STUDY DESIGN

#### 3.1 General Description

This is an open-label, multicenter study, consisting of a conditional PN/IV optimization period, a mandatory PN/IV stabilization period, and a 24-week treatment period. A schematic representation of the study design is presented in [Figure 1](#).

**Figure 1: Study Schematic**

##### 3.1.1 Optimization and Stabilization Periods

If at screening, a subject does not have an optimized PN/IV volume, defined as a 48-hour urine output between 2 and 4 L, he/she will enter the optimization period, during which the minimally tolerated stable PN/IV volume will be determined during a period of up to 8 weeks.

All subjects will then enter the stabilization period, during which the target PN/IV volume will be maintained for at least 4 consecutive weeks (8 weeks maximum). Those subjects who fail to stabilize will not proceed further and will not be included in the treatment period.

Schedules of evaluations for the optimization/stabilization period can be found in the protocol.

